Aim 2: Examine the efficacy of the FCU-Online intervention by conducting a randomized, controlled trial of 300 at-risk middle school youths. Research suggests that a live coach enhances outcomes associated with web-based interventions; however, a web-based intervention that requires no coaching can be widely disseminated and has greater potential for a large public health impact. We will examine outcomes associated with a web/ mobile + coach version and a web/ mobile-only version of the FCU. Families will be randomly assigned to the FCU-Online intervention (100 web/ mobile+coach, 100 web/mobile-only) or a waitlist control group that receives middle school as usual for 12 months and then access to the web/mobile only condition (n=100).

Version 3.18.19

Aim 2.1: Evaluate main effects of both versions of the FCU-Online, including academic achievement, behavioral control, family cohesiveness, and delayed onset of substance use.

Aim 2.2: Test a developmental, mediational model in which parenting skills and behavior mediate changes in youth behavior over time. It is expected that families who receive the FCU will show reductions in growth of youths' risk behavior, compared with the waitlist control group. Reductions will be mediated by positive changes in parenting behaviors and parenting skill development.

Aim 2.3: Examine moderators, including gender, ethnicity, and socioeconomic status, and model intervention effects by testing moderators over time. We will assess the feasibility of the FCU as an internet-delivered intervention in middle schools, the extent to which participants engaged in the intervention and complete the program, satisfaction with the program, and effects of the FCU on improved parenting skills, positive youth adjustment, and reductions in youth problem behavior over two years.

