Because the focus of the implementation study is school staff rather than parents, we will not be collecting baseline surveys or any of the follow-up surveys used in the main research study. Rather, parents will be identified by coaches, and enrolled directly in the website. After providing informed consent, parents will complete a qualtrics form that includes the information needed to enroll them in the website. The data provided via this form will be sent directly to research staff, who will use it to enter participants into the administrative website that triggers an email to participants thanking them for their willingness to participate and includes log-in information and directions for how to get started. Parents will complete the survey that is built into the website, receive computer generated feedback, and will then meet with their coach to discuss the feedback and the parenting modules presented on the website. The survey takes about 30 minutes to complete; parents may log-in and use the parenting resources as little or as often as they would like.

At the end of the study, parents will be asked to complete a 2-page Website Satisfaction Survey which will take about 10 minutes to complete. This survey will be administered via Qualtrics. An email with a link to the survey will be sent to parents approximately 6 months after they are enrolled in the study.

At the end of the study, coaches will be interviewed one-on-one by a member of the research team about the ways that they were able to use the website to work with families, any challenges that they encountered, and their insights into factors that could be improved to enhance implementation in schools. This interview will take approximately 1 hour.

Analysis

For our preliminary analyses, we will compare baseline characteristics of participants across conditions to test for significant differences; characteristics that differ across conditions will be used as covariates in subsequent analyses. Logistic regression analyses will be used to examine potential differences by study condition between dropouts and continuing participants on baseline measures. Attrition analyses will provide information about the external validity of the study, and interaction effects between condition and predictors will provide information about potential confounding effects (Cook & Campbell, 1979).

Aim 1: Design and evaluate a web-based FCU intervention that is guided by feedback from focus groups.

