Aim 2.1: Analysis of main effects. The hypotheses tested in this aim are (a) families in each intervention condition will show significant improvements on the outcome variables, compared with youths in the control condition, and (b) families assigned to the web/mobile+ coach condition will have significantly better outcomes compared with those assigned to the web/mobile-only condition. The primary outcomes include academic competence, youth behavioral control, delayed onset of youth substance use, reduced family conflict, increased family cohesion, and positive family relationships. The secondary outcomes include the putative mediating mechanisms of parenting skills and behaviors. Families will be randomized to condition and will be the unit of analysis for all models. Mixed-effects analyses will be based on a hierarchical linear modeling approach in which students are nested within schools, primary outcomes are nested within individual students at Level 1 of the model, and between-subject predictors (fixed effects), such as treatment condition and child/parent demographics, will be examined at Level 2. For each of the three pairwise contrasts between conditions, intervention effects will be examined by modeling longitudinal trajectories across time with mixed-effects models using SAS PROC MIXED or mPlus software.

Aim 2.2: Mediation model testing. We will test whether change in the putative mediating mechanisms of parenting skills and behaviors (e.g., change from baseline to 3-month follow-up) mediate the association between study conditions and longitudinal trajectories of the youth and family outcomes.

Aim 2.3: Examine moderating effects and intervention process measures. The moderation analyses will follow recommendations by Kraemer and colleagues (2002) and analytic methods of Aiken and West (1991), Jaccard and Turrisi (2003), and Preacher et al. (2006). Because we do not have specific hypotheses

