Official Title: Prevention of Substance Use in At-Risk Students: A Family-Centered Web Program

NCT Number: NCT03060291

Document Date: July 14, 2020

Statistical Analysis Plan with Results Information

Data Analysis

Preliminary analyses included descriptive statistics and plots to screen outcomes for normality. Chi-square statistics and one-way ANOVA models were used to compare study condition and demographic characteristics between participants who dropped out of the study versus those who completed all four assessments.

Intent-to-treat analyses of condition effects were evaluated with mixed effects growth models using SAS 9.2 PROC MIXED and estimated using full-information maximum likelihood, an unstructured variance and covariance matrix, and random intercepts and slopes. Variability in outcomes from pretest to 1-year follow-up was modeled as a function of condition, time (coded in months), and a condition \times time interaction term. The intercept was specified at the 1-year follow-up assessment; thus, the condition effect is a test of whether intervention groups differed at the end of the study. Following Singer and Willet (2003), when constructing the longitudinal model we (a) examined empirical growth plots; (b) fit an unconditional means model; (c) fit an unconditional linear growth model; (d) fit unconditional non-linear models; and (e) compared models of longitudinal change using the Akaike Information Criterion. Three a priori dummy coded comparisons were examined: wait-list control (reference group) versus web-only, wait-list control (reference group) versus web plus coach, and web-only (reference group) versus web plus coach. Effect sizes for the condition effect at the end of the study are reported as Cohen's d (Cohen, 1988) and computed as model estimated differences in the outcomes at 1-year follow-up divided by the observed baseline pooled standard deviation.

Results

Preliminary analyses. Demographic make-up of the sample, program use metrics, baseline equivalency of the three intervention groups, and correlations of the pretest measures

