have been previously reported (Stormshak et. al., 2019). Briefly, parents in the study were predominately female, on average 40.0 ($SD = 6.1$) years of age, and 35% had a 4-year college degree or graduate training. The children in the study were approximately gender balanced, mostly white, and mostly lived in suburban environments. Use of the site was robust, but the web plus coach group used the program significantly more than the web-only group. Participants in the three conditions did not differ on gender, area (rural, suburban, urban), minority status, SES risk score or pretest measures of the outcomes indicating randomization produced initially equivalent groups. The correlations of the pretest measures ranged from $r = -.67$ to $r = .60$ (mean $|r| = .30$).

The outcomes approximated normal distributions except conduct problems which was normalized with a logarithmic transformation. Complete data was available for 88% of the sample and attrition was 6% at posttest, 8% at 6-month follow-up and 9% at 1-year follow-up. Number of assessments completed was not significantly associated with study condition, child's gender and child's race (all p -values $> .08$). Comparison of linear and non-linear unconditional models showed a linear model had superior fit to a linear and quadtric model for all study outcomes.

Table 1 provides means and standard deviations for the outcomes at each assessment point for each of the three conditions. Table 2 provides a summary of the condition effects from the growth models for the three a priori comparisons and is a test of whether groups differed in change in outcomes from pretest to the 1-year follow-up. No statistically significant (at $p < .017$) differences were found, although one trend-level effect ($p < .10$) is worth noting. The web plus coach group showed trend level differences in sense of parenting importance that favored the

web plus coach group relative to the wait-list control group, a small to medium effect (p -value = .081, $d = .28$), a small to medium effect (Cohen, 1988).

	Pretest		3-Month Posttest		6-Month Follow-up		1-Year Follow-up	
	M	SD	M	SD	M	SD	M	SD
Wait-list control	1.05	1.38	1.24	1.54	1.00	1.44	1.08	1.45
Web-only intervention	1.37	1.81	1.32	1.63	1.17	1.57	1.19	1.40
Web plus coach intervention	1.44	1.65	1.30	1.55	1.12	1.54	1.21	1.60
Hyperactivity								
Wait-list control	3.45	2.69	3.31	3.43	3.24	2.32	3.46	2.56

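### Table 2 tests a 1-year difference in level but is described as a test of change; the condition × time result is not reported and no pretest adjustment is stated.

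*SAP*

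**What the plan says.** SAP, Data Analysis: the growth model contains condition, time in months and their interaction, with random intercepts and slopes. "The intercept was specified at the 1-year follow-up assessment", and so "the condition effect is a test of whether intervention groups differed at the end of the study". Cohen's d is tied to the same quantity, being "computed as model estimated differences in the outcomes at 1-year follow-up divided by the observed baseline pooled standard deviation". No pretest covariate and no common pretest mean is listed; the pretest enters as the first of four repeated outcomes.

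SAP, Results, in the paragraph introducing the tables: Table 2 summarises the condition effects and "is a test of whether groups differed in change in outcomes from pretest to the 1-year follow-up". Table 2 is titled as the condition parameter and has one row per outcome and contrast (7 × 3 = 21). It has no condition × time rows, and the Results text gives no such estimate either.

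Protocol, section C, Analysis, Aim 2.1: for each pairwise contrast, "intervention effects will be examined by modeling longitudinal trajectories across time with mixed-effects models". Section B, Aim 2.2: "It is expected that families who receive the FCU will show reductions in growth of" risk behaviour, relative to the waitlist group. On covariates, the preliminary-analysis paragraph says "characteristics that differ across conditions will be used as covariates in subsequent analyses". The SAP then reports that the arms did not differ on the pretest measures.

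**The concern.** The two SAP sentences give one coefficient two meanings. With time centred at month 12, the condition coefficient is the difference between arms in fitted level at month 12. The difference in change is carried by condition × time. That term is in the fitted model and bears directly on the Protocol's language of trajectories and growth, but it is not shown.

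A reader of the Results would conclude that no outcome changed differently between arms, which Table 2 did not test. The distinction would matter little if the arms had started level. On the readable part of Table 1 they did not: the coach arm had higher (worse) pretest scores than wait-list on all three problem scales. A 12-month level contrast without baseline adjustment carries that chance gap, which leans against the coach arm on these scales, and it can also lose precision.

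**Working it through.** **Inputs.** Means and SDs at 0, 3, 6 and 12 months are from SAP Table 1; estimates and SEs are from SAP Table 2. Contrasts are the second-named arm minus the first. The first block of Table 1 rows has no label in the available text and is taken to be conduct problems. Rows for the other four outcomes are not available. Assumed: 91 per arm (100 planned, less 9% attrition at 1 year) and a pretest-to-1-year correlation r of .3, .5 or .7, since none is given.

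**1. Reproducing a stated figure.** Emotional problems, coach vs wait-list: baseline pooled SD = √((2.27² + 2.12²)/2) = 2.196, and −0.47/2.196 = −0.214, against a stated d of −0.21. So d is the Table 2 estimate over the baseline SD, as the SAP defines it.

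**2. Level or change?** Level = difference in 12-month means. Change = level minus the pretest difference.

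| Outcome, contrast | Table 2 | Level | Change | Gap to level | Gap to change |
|---|---|---|---|---|---|
| Hyperactivity, web-only vs wait-list | −0.17 | −0.25 | −0.52 | 0.08 | 0.35 |
| Hyperactivity, coach vs wait-list | 0.22 | −0.05 | −0.79 | 0.27 | 1.01 |
| Hyperactivity, coach vs web-only | 0.36 | 0.20 | −0.27 | 0.16 | 0.63 |
| Emotional, web-only vs wait-list | 0.06 | 0.04 | −0.18 | 0.02 | 0.24 |
| Emotional, coach vs wait-list | −0.47 | −0.51 | −0.95 | 0.04 | 0.48 |
| Emotional, coach vs web-only | −0.51 | −0.55 | −0.77 | 0.04 | 0.26 |

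All six lie nearer to level. Because the SAP model is linear, the check was repeated with an unweighted straight line through the four mean differences. The gaps are then 0.04–0.33 to level and 0.13–0.89 to change, again nearer to level in all six. Conduct problems are left out because Table 2 is on a log scale.

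**3. Pretest gaps, coach minus wait-list.** Conduct (assumed) 0.39/1.521 = 0.26 SD; hyperactivity 0.74/2.781 = 0.27 SD; emotional problems 0.44/2.196 = 0.20 SD.

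**4. Approximate tests of change, emotional problems.** Change-score SE = √(Σ over the two arms of (SD0² + SD12² − 2r·SD0·SD12)/91). Slope = 12 × the least-squares slope through the four mean differences, with correlation r between all visits.

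| Contrast | Measure | Estimate | p at r = .3 / .5 / .7 |
|---|---|---|---|
| Coach vs wait-list | change score | −0.95 | .013 / .003 / .0002 |
| Coach vs wait-list | slope × 12 | −0.77 | .035 / .013 / .001 |
| Coach vs web-only | change score | −0.77 | .047 / .019 / .002 |
| Coach vs web-only | slope × 12 | −0.70 | .057 / .024 / .004 |

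**5. Approximate baseline-adjusted 12-month contrast.** Estimate = D12 − r(SD12/SD0)D0, and SE = SD12·√((1 − r²)(2/n + D0²/((2n − 2)SD0²))), with n = 91 and 2n − 3 = 179 df. For emotional problems, coach vs wait-list, SD12 = √((2.37² + 1.96²)/2) = 2.175. At r = .5 the estimate is −0.51 − 0.5 × (2.175/2.196) × 0.44 = −0.73 with SE 0.28, so p = .010.

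The more cautious version starts from the Table 2 estimate and uses the line-fit pretest gap (0.19 for coach vs wait-list, 0.15 for coach vs web-only), with SE = SD12·√((1 − r²)·2/n).

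| Emotional problems | Reported p | Start | p at r = .3 / .5 / .7 | p = .017 at r = |
|---|---|---|---|---|
| Coach vs wait-list | .127 | Table 1 | .040 / .010 / .0005 | .44 |
| | | Table 2 | .089 / .045 / .010 | .65 |
| Coach vs web-only | .101 | Table 1 | .050 / .021 / .003 | .53 |
| | | Table 2 | .077 / .040 / .009 | .64 |

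Scaling Table 2's own SE by √(1 − r²) moves the .65 to .59. At r = .3 there is no gain in precision for coach vs wait-list (SE 0.31 against the reported 0.30).

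**6. Where nothing changes.** Coach vs wait-list on raw-scale conduct stays null (p = .95/.74/.38). Hyperactivity from Table 1 gives p = .49/.24/.055 and needs r = .78 to reach .017; from Table 2 it gives p = .85/.92/.61.

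**The case against.** The level contrast is unbiased under randomisation, and the Data Analysis section declares it openly. The growth sentence in the Protocol sits under the mediation aim; the main-effect hypotheses in Aim 2.1 speak of improvements and better outcomes, which a 1-year contrast can fairly address. The Protocol adjusts only for characteristics that differ between arms, and the SAP reports none, so leaving the pretest unadjusted is not a departure from plan. All of this stands. It does not make the Results sentence right or supply the missing interaction, and a non-significant baseline test neither removes a 0.20–0.27 SD gap nor turns a level test into a change test.

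The adjusted p-values are also open to challenge, and these limits stand too. The correlation r is unknown. Only two of the nine readable contrasts cross .017 within r = .3 to .7, and they were picked out after seeing 21 results. The .017 threshold covers three contrasts for one outcome; at .05/21 = .0024 the Table 1 version needs r = .62 (coach vs wait-list) or .71 (coach vs web-only). The six comparisons in step 2 are not independent, since each outcome's three contrasts share arms. One barely discriminates on the line fit (emotional problems, web-only vs wait-list: 0.09 against 0.13). Table 2's +0.22 for hyperactivity, coach vs wait-list, is not reproduced by the Table 1 level of −0.05, so nothing is inferred from its sign.

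**Conclusion.** The concern holds and should be fixed. The contradiction between the two SAP sentences and the absence of any condition × time result need no assumption. Table 1 supports the level reading for the six estimates that can be checked; four of the seven outcomes cannot be checked.

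The practical size is conditional. On 91 per arm and r between .3 and .7, the two emotional-problems contrasts involving the coach arm could move across .017 under baseline adjustment, depending on r and on the starting figures. The other readable contrasts stay above .017 on the same adjustment. These are approximations from summary statistics and do not replace the fitted model. They show that the null statement about change is untested, not that it is false. The level analysis remains a valid, if less precise, estimate of the 1-year effect.

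**What to change.** 1. Reword the Results sentence so that Table 2 is described as the difference between arms in level at 1 year.
2. Report the condition × time estimate, SE and p-value for all seven outcomes and three contrasts. The term is already in the model.
3. Add a baseline-adjusted 12-month contrast for all seven outcomes, using either a common pretest mean with visit as a category (0, 3, 6, 12 months) or the pretest as a covariate. Apply it whatever the baseline significance tests show. Label it post hoc, and keep the existing Table 2 beside it.

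The cost is one corrected sentence and one re-run on existing data. The drawback is that the adjusted results were chosen after the data were seen and must be read that way. The categorical-visit option also sets aside the linear form that the SAP selected by model comparison, which is a further reason to present it as an addition and not a replacement.
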